### 13.1. DERIVATIONS

The date of first and last trial medication administration will be taken from the eCRF “Self-Administration of trial medication” page. Interruptions, compliance, and dose changes are not taken into account for duration of exposure.

**Duration of exposure (weeks)** = (date of last injection - date of first injection + 1)/ 7.

**Duration of exposure (days)** = (date of last injection - date of first injection + 1).

---

Document: \\ieedc-nas01a\BIOSdata\Boehringer\_Ingelheim\BI\_695501\NVA96235\Biostatistics\Documentation\SAP\10  
v1.0\BI\_1297.3\_SAP\_22JUN2016\_v1.0

Author: Version Number: 1.0  
Version Date: 22JUN2016

Template No: CS\_TP\_BS016 – Revision 3  
Effective Date: 01May2012

Reference: CS\_WI\_BS005

---

Patient Year Exposure (year) = cumulative duration of exposure in days per subjects / 365.25

## 14. TRIAL MEDICATION COMPLIANCE

Compliance to trial medication will be presented for the FAS and SAF.

A first calculation will be based on the count of syringe boxes and/or labels in the eCRF. A second calculation will take into account the approximate left-over percentage of the pre-filled syringe volume in case the full volume was not injected.

Descriptive statistics for drug accountability compliance overall, overall until Week 12 and overall until Week 24 will be presented.

Descriptive statistics for pre-filled syringe volume compliance will be presented at each planned visit, overall, overall until Week 12 and overall until Week 24.

### 14.1. DERIVATIONS

Compliance will be calculated for subjects having attended the visit. A subject is considered having attended the visit if the indicated visit is captured in the eCRF database. Two types of compliances will be computed: drug accountability compliance and compliance (based on the left-over percentage of the pre-filled syringe volume).

#### Drug accountability compliance

Compliance with trial medication—based on the drug accountability data—will be calculated as the number of syringes injected (total dispensed – total unused + administered at site) divided by the prescribed number of syringes expressed as a percentage, see calculations below. The number of syringes will be captured in the two eCRF pages: Self-Administration of trial medication (if the administration was on site) and Trial medication Dispensation and collection (if the administration was at patient's home). The number of syringes required to be taken per week is 0.5.

- Overall Compliance by Week 12 and Overall Compliance by Week 24 will include unscheduled visit data and will be calculated by:
  1. Summing the number of syringes dispensed until 12 (resp. 24) Weeks exclusively and the number of syringes administered on site until 12 (resp. 24) Weeks inclusively, and subtracting the number of syringes unused until 12 (resp. 24) Weeks inclusively
  2. Multiplying by two the above quantity and dividing by the number of weeks between the first administration date and visit date Week 12 (resp. 24) plus 2 weeks
  3. Multiplying by 100 to express compliance as a percentage.

For subjects who permanently stop the trial medication prior to Week 12 (resp. 24), the "Date of Visit X(n)" will be replaced by the date of last administration of trial medication.

---

Document:	\ieedc-nas01a\BIOSdata\Boehringer_Ingelheim\BI_695501\NVA96235\Biostatistics\Documentation\SAP\10\v1.0\BI_1297.3_SAP_22JUN2016_v1.0		
Author:	Version Number:	1.0	Version Date: 22JUN2016

Template No: CS\_TP\_BS016 – Revision 3  
Effective Date: 01May2012

Reference: CS\_WI\_BS005

- Overall Compliance to trial medication will include unscheduled visit data and will be calculated by:
  1. Summing the number of syringes dispensed over the study, the number of syringes administered on site over the study, and subtracting the number of syringes unused over the study
  2. Multiplying by two the above quantity and dividing by the number of weeks between the first and last administration date plus 2 week
  3. Multiplying by 100 to express compliance as a percentage.

#### Compliance

Compliance with trial medication will be based on the “Self-Administration of trial medication” eCRF data.

The amount of drug to be administered is 0.8mL. The compliance will be based on the approximated left-over percentage of the pre-filled syringe volume in % (eCRF data) and the total volume (0.8mL considered as 100%) and calculated as amount of drug administered divided by the amount of drug to be administered expressed as a percentage, see calculations below. If the administration of trial medication occurred at home, one will assume 100% of the volume was administered if the administration occurred (i.e. “Was trial drug administered?” reported as “Yes”).

- “Per Visit” Compliance to trial medication will be calculated at every administration timepoint as follows:

Compliance (%) =  $100 - \text{Approximated left-over percentage of the pre-filled syringe volume as indicated in eCRF.}$

- Overall Compliance by Week 12 and Overall Compliance by Week 24 will be calculated as mean of the “per visit” compliance until Week 12 (resp. Week 24).
- Overall Compliance to trial medication will be calculated as mean of the “per visit” compliance.

## 15. EFFICACY OUTCOMES

### 15.1. PRIMARY EFFICACY

No primary efficacy endpoint.

### 15.2. SECONDARY EFFICACY

The secondary efficacy analyses will be performed for the FAS and are summarized below:

Document:	\ieedc-nas01a\BIOSdata\Boehringer_Ingelheim\BI_695501\NVA96235\Biostatistics\Documentation\SAP\10\\v1.0\BI_1297.3_SAP_22JUN2016_v1.0		
Author:	Version Number:	1.0	Version Date:
Template No: CS_TP_BS016 – Revision 3			Reference: CS_WI_BS005
Effective Date: 01May2012			22JUN2016
Copyright © 2012	. All rights reserved.	Unauthorized use, disclosure or	
The contents of this document are confidential and proprietary to			
reproduction is strictly prohibited.			

Secondary endpoints	Population, imputation method	Analysis
Change from Baseline of DAS28(ESR) at Week 48	FAS, LOCF	Descriptive
Proportion of subjects meeting the ACR20 response criteria at Week 48	FAS, NRI/LOCF	Descriptive
Proportion of subjects who meet the ACR/EULAR definition of remission at Week 48	FAS, no imputation method	Descriptive
Proportion of subjects with EULAR response at Week 48	FAS, no imputation method	Descriptive

### **15.2.1. SECONDARY EFFICACY VARIABLES & DERIVATIONS**

#### **15.2.1.1. DAS28 endpoint**

A secondary endpoint is:

- The change from Baseline in trial 1297.2 in DAS28 (ESR) at Week 48 of trial 1297.3

DAS28 (ESR) score will be derived at every planned efficacy assessment visit using the formula described in section 10.1. The change from Baseline in DAS28 (ESR) (baseline-post baseline) will be calculated for every planned post-baseline efficacy assessment visit.

#### **15.2.1.2. ACR20 endpoint**

A secondary efficacy endpoint is

- The proportion of subjects meeting the ACR20 response criteria (based on improvement since Baseline in trial 1297.2) at Week 48 of trial 1297.3.

ACR20 response will be calculated at every planned efficacy assessment visit.

A subject has an ACR20 response if all of the following occur:

- A  $\geq 20\%$  improvement in the swollen joint count (66 joints)
- A  $\geq 20\%$  improvement in the tender joint count (68 joints)
- A  $\geq 20\%$  improvement in at least three of the following assessments:
  - Patient's assessment of pain
  - Patient's global assessment of disease activity
  - Physician's global assessment of disease activity (see below for more details).
  - Patient's assessment of physical function, as measured by the Health Assessment

---

Document: \\ieedc-nas01a\BIOSdata\Boehringer\_Ingelheim\BI\_695501\NVA96235\Biostatistics\Documentation\SAP\10\\v1.0\BI\_1297.3\_SAP\_22JUN2016\_v1.0

Author: Version Number: 1.0  
 Version Date: 22JUN2016

Template No: CS\_TP\_BS016 – Revision 3  
 Effective Date: 01May2012

Reference: CS\_WI\_BS005

## Questionnaire – Disability Index (HAQ-DI)

- Acute phase reactant (CRP).

Improvement is assessed as the decrease in a component relative to baseline,  $(100 \times (\text{baseline} - \text{post baseline}) / \text{baseline})$ .

The handling of retests, unscheduled and end of trial measurements is described in Section 6.3.

If a joint evaluation is missing or 'Not done' at baseline (please refer to section 6.2 for baseline definition), it will not contribute to the joint counts at baseline and all subsequent visits (i.e., will be treated as 'Not Done'). If at least half but not all joints are evaluable (at least 33 joints for the 66 joint count for swelling with eCRF values 'present' or 'absent', at least 34 joints for the 68 joint count for tenderness with eCRF values 'present' or 'absent'), then the observed prorated tender/swollen joint count will be calculated.

The prorated scores will be evaluated based upon the number of evaluable joints: the counted score will be multiplied by 66 for swelling or 68 for tender joint count and divided by the number of joints evaluated. For example, for tender joint count, if only 45 of the 68 joints are assessed at a visit and 18 of those 45 are tender (eCRF value 'present'), the prorated tender joint count is  $18/45 \times 68 = 27.2$ . This exact value, 27.2 (and not 18) will be used for ACR20 score calculation. For swollen joint count, if only 45 of the 66 joints are assessed at a visit and 18 of those 45 are swelling (eCRF value 'present'), the prorated swollen joint count is  $18/45 \times 66 = 26.4$ . This exact value, 26.4 (and not 18) will be used for ACR20 score calculation.

If less than half of the joints are evaluable (eCRF value 'not done' or missing), the number of tender/swollen joints is missing.

The central laboratory data for CRP and eCRF data for all other ACR20 components will be used for the calculation.

Patient's assessment of pain as well as patient's and physician's global assessment of disease activity accessed using the VAS of 100 mm.

**Patient's assessment of physical function** will be assessed using HAQ-DI. The calculation of this index is described below. The HAQ-DI is composed of 20 items. There are eight categories, each of which has at least two component questions:

1. Dressing and grooming
2. Arising
3. Eating
4. Walking
5. Hygiene
6. Reach
7. Grip
8. Common daily activities.

For each of the categories, subjects report the amount of difficulty they have in performing two or three specific sub-category items, or also known as components, or component variables.

---

Document: \\ieedc-nas01a\BIOSdata\Boehringer\_Ingelheim\BI\_695501\NVA96235\Biostatistics\Documentation\SAP\10  
v1.0\BI\_1297.3\_SAP\_22JUN2016\_v1.0

Author: Version Number: 1.0  
Version Date: 22JUN2016

Template No: CS\_TP\_BS016 – Revision 3  
Effective Date: 01May2012

Reference: CS\_WI\_BS005

0 = without ANY difficulty

1 = with SOME difficulty

2 = with MUCH difficulty

3 = UNABLE to do.

If a component question is left blank, then the score for that category is determined by the remaining completed question(s).

The subject must have a score for at least 6 of the 8 categories. If there are less than 6 categories completed, a HAQ-DI cannot be computed, whether the missing categories are due to missing values or they do not apply to the respondent.

**Calculation of HAQ-DI score:**

1. Sum the eight category scores\*

\*A category score is determined from the highest score of the sub-categories, or components, in that category, except when aids or devices are taken into account (see below). For example, if there are three sub-category items (as in the category ARISING), and the subject responds with a 1, 2, and 0, respectively, to the three sub-category items, the score for the ARISING category will be a 2.

2. Divide the sum by the number of categories answered (range - 6-8)

Scoring AIDS OR DEVICES or help companion variables:

1. When there are NO aids or devices, or help indicated for a category, the category's score is not modified.
2. When aids or devices or help ARE indicated by the subject, the score for the category item is raised from a 0 or a 1 to a 2, but if the subject's highest score for that sub-category is a 2, it stays a 2 (the same for 3)

#### 15.2.1.3. ACR/EULAR remission

A secondary efficacy endpoint is

- The proportion of subjects who meet the ACR/EULAR definition of remission (based on improvement since Baseline in trial 1297.2) at Week 48 of trial 1297.3.

To have the ACR/EULAR Remission, the subject must satisfy all of the following criteria:

- Tender joint count (TJC) (68)  $\leq$  1
- Swollen joint count (SJC) (66)  $\leq$  1
- CRP  $\leq$  1mg/dL
- Patient global assessment  $\leq$  10 (on a 0-100 scale)

#### 15.2.1.4. EULAR response

A secondary efficacy endpoint is

---

Document: \\ieedc-nas01a\BIOSdata\Boehringer\_Ingelheim\BI\_695501\NVA96235\Biostatistics\Documentation\SAP\10  
v1.0\BI\_1297.3\_SAP\_22JUN2016\_v1.0

Author: Version Number: 1.0  
Version Date: 22JUN2016

Template No: CS\_TP\_BS016 – Revision 3  
Effective Date: 01May2012

Reference: CS\_WI\_BS005

- The proportion of subjects with EULAR response (good response, moderate response or no response) (based on DAS28 (ESR) improvement since Baseline in trial 1297.2) at Week 48 of trial 1297.3.

Improvement in DAS28 (ESR) will also be categorized using the EULAR response criteria:

DAS28 Improvement			
DAS at endpoint	≥1.2	>0.6 and <1.2	≤0.6
≤3.2	Good Response	Moderate response	No Response
>3.2 and ≤5.1	Moderate response	Moderate response	No Response
>5.1	Moderate response	No Response	No Response

Where DAS28(ESR) improvement is computed as:

- DAS28(ESR) at 1297.2 baseline – DAS28(ESR) at Week X.

### 15.2.2. MISSING DATA METHODS FOR SECONDARY EFFICACY VARIABLES

#### 15.2.2.1. Missing data method for DAS28

Last observation carried forward (LOCF) will be used for imputation of missing component variables prior to DAS28 (ESR) score calculation.

#### 15.2.2.2. Missing data method for ACR20

Missing ACR20 data will be imputed at Week 48 using a combination of non-responder imputation and LOCF methods.

Table 1 details exactly where the LOCF / NRI imputation will be applied.

Table 1: Application of LOCF/NRI for the primary analysis on the FAS – possible outcomes

Analysis (FAS)	...prior to week X	
	Discontinued treatment #	Did NOT discontinue treatment
ACR20 computable using observed data at week X	No (NRI applied)	Yes/No (observed)
ACR20 NOT computable using observed data at week X	No (NRI applied)	Yes/No (LOCF applied)\$

# lost to follow-up from trial is also included here, or patients who took a therapy that may significantly impact efficacy assessment prior to this time-point.

The following steps will be followed:

Step 1: Missing ACR20 component data will be imputed using the last observation carried forward (LOCF) method

Document:	\\ieedc-nas01a\BIOSdata\Boehringer_Ingelheim\BI_695501\NVA96235\Biostatistics\Documentation\SAP\10\v1.0\BI_1297.3_SAP_22JUN2016_v1.0	Version Number:	1.0
Author:		Version Date:	22JUN2016

Template No: CS\_TP\_BS016 – Revision 3  
 Effective Date: 01May2012

Reference: CS\_WI\_BS005

and ACR20 will be calculated based on the imputed component data.

Last observation will be carried forward as many time as needed.

Step 2: The imputed ACR20 will be set to non-responder at Week 48, if the subject

- discontinue treatment prior to Week 48
- are lost-to-follow-up prior to Week 48
- have any severe violation related to any therapy that may significantly impact efficacy assessment prior to Week 48

Severe violation related to any therapy (according to CTP Table 4.2.2.1: 1) that may significantly impact efficacy assessment will be assessed by:

- providing to the trial medical advisor
  - a list of medication codes (WHO Drug Dictionary version SEPR2015 or higher) presented in CTP Table 4.2.2.1: 1 and taken by at least one subject during trial conduct.
  - full individual concomitant medication information including dose, frequency and Study day at start of medication.
- Trial medical advisor will then identify the medications and start date of severe violation which may impact efficacy assessment

#### 15.2.2.3. Missing data method for ACR/EULAR remission and EULAR response

Efficacy data for ACR/EULAR remission and EULAR response will not be imputed.

### 15.2.3. ANALYSIS OF SECONDARY EFFICACY VARIABLES

Secondary efficacy endpoints will be presented for FAS.

Descriptive statistics will be provided for each secondary endpoint.

---

Document: \\ieedc-nas01a\BIOSdata\Boehringer\_Ingelheim\BI\_695501\NVA96235\Biostatistics\Documentation\SAP\10  
v1.0\BI\_1297.3\_SAP\_22JUN2016\_v1.0

Author: Version Number: 1.0  
Version Date: 22JUN2016

Template No: CS\_TP\_BS016 – Revision 3  
Effective Date: 01May2012

Reference: CS\_WI\_BS005

---

Document: \\ieedc-nas01a\BIOSdata\Boehringer\_Ingelheim\BI\_695501\NVA96235\Biostatistics\Documentation\SAP\10  
v1.0\BI\_1297.3\_SAP\_22JUN2016\_v1.0

Author: Version Number: 1.0  
Version Date: 22JUN2016

Template No: CS\_TP\_BS016 – Revision 3  
Effective Date: 01May2012

Reference: CS\_WI\_BS005

---

Document: \\ieedc-nas01a\BIOSdata\Boehringer\_Ingelheim\BI\_695501\NVA96235\Biostatistics\Documentation\SAP\10  
v1.0\BI\_1297.3\_SAP\_22JUN2016\_v1.0

Author: Version Number: 1.0  
Version Date: 22JUN2016

Template No: CS\_TP\_BS016 – Revision 3  
Effective Date: 01May2012

Reference: CS\_WI\_BS005

---

Document: \\ieedc-nas01a\BIOSdata\Boehringer\_Ingelheim\BI\_695501\NVA96235\Biostatistics\Documentation\SAP\10  
v1.0\BI\_1297.3\_SAP\_22JUN2016\_v1.0

Author: Version Number: 1.0  
Version Date: 22JUN2016

Template No: CS\_TP\_BS016 – Revision 3  
Effective Date: 01May2012

Reference: CS\_WI\_BS005

## 16. SAFETY OUTCOMES

All outputs for safety outcomes will be based on the SAF.

There will be no statistical comparisons between the treatment groups for safety data, unless otherwise specified with the relevant section.

The primary endpoint is defined as:

---

Document: \\ieedc-nas01a\BIOSdata\Boehringer\_Ingelheim\BI\_695501\NVA96235\Biostatistics\Documentation\SAP\10  
v1.0\BI\_1297.3\_SAP\_22JUN2016\_v1.0

Author: Version Number: 1.0  
Version Date: 22JUN2016

Template No: CS\_TP\_BS016 – Revision 3  
Effective Date: 01May2012

Reference: CS\_WI\_BS005

---

- The number (proportion) of patients with drug-related AEs during the treatment phase (with onset date between start of treatment and 10 weeks after the last dose of trial medication, i.e. treatment-emergent AE, refer to Section 16.1.1.1).

Other safety endpoints will be:

- The proportion of patients with infections/serious infections (seriousness of infection defined as requirement of i.v. antibiotics for treatment and/or meeting seriousness criteria to be qualified as an SAE)
- The proportion of patients who experience hypersensitivity reactions
- The proportion of patients who experience DILI
- The proportion of patients with injection-site reactions
- The proportion of patients with antidrug antibodies (ADAs) at Week 12, Week 24, and Week 48
- The proportion of patients with neutralizing antidrug antibodies (nABs) at Week 12, Week 24, and Week 48
- The proportion of patients who discontinue due to a drug-related AE

Other safety evaluations will include: physical examination, vital signs (blood pressure, pulse rate, respiratory rate, body temperature), 12-lead ECGs, laboratory tests, and continuous AE monitoring.

## 16.1. ADVERSE EVENTS

Adverse Events (AEs) will be coded using the MedDRA central coding dictionary, Version 18.1 or higher. The system organ classes will be sorted by internationally agreed EMA SOC order (refer to APPENDIX 3), preferred terms will be sorted by decreasing frequencies (within system organ class).

An overall summary of the number of subjects, percentages, number of events and patient-year incidence rate within each of the categories described in the sub-section below will be provided.

In case of worsening in severity, a new entry is created with start date equal to start of worsening.

All the outputs described in this section will be presented according to the initial randomization and re-randomization of trial 1297.2 unless specified otherwise.

Listings will include treatment-emergent adverse events (TEAEs) and Non-TEAEs.

---

Document: \\ieedc-nas01a\BIOSdata\Boehringer\_Ingelheim\BI\_695501\NVA96235\Biostatistics\Documentation\SAP\10  
v1.0\BI\_1297.3\_SAP\_22JUN2016\_v1.0

Author: Version Number: 1.0  
Version Date: 22JUN2016

Template No: CS\_TP\_BS016 – Revision 3  
Effective Date: 01May2012

Reference: CS\_WI\_BS005

### 16.1.1. ADVERSE EVENT SPECIFIC DERIVATION

#### 16.1.1.1. Treatment Emergent Adverse Event

Treatment-emergent adverse events (TEAEs) are defined as AEs that started or worsened in severity on or after the first dose of 1297.3 trial medication and prior to the last date of 1297.3 trial medication + 10 weeks inclusive.

Non-TEAEs will be classified as "Prior treatment" if AE start date is strictly prior the first injection date. Non-TEAEs will be classified as "Post treatment" if AE start date is strictly after the last injection date + 70 days.

See APPENDIX 2 for handling of partial dates for AEs. In the case where it is not possible to define an AE as treatment-emergent or not, the AE will be classified by the worst case; i.e. treatment-emergent.

#### 16.1.1.2. Patient-Year incidence rate

Patient-year incidence rate per 1000 years for AEs will be calculated as follows:

(Number of subjects with at least one AE) / (Patient-Year) \* 1000

where Patient-Year is the sum of time at risk for each subject (days) in the treatment group divided by 365.25.

The time at risk (years) per subject is derived as following:

- subject had at least one AE with specific criterion:

time at risk (days) = start date of first AE meeting the specific criterion – start of treatment +1

- subject without AE with specific criterion:

time at risk (days) = end of treatment + 70 – start of treatment +1

Patient-year incidence rate per 1000 years for TEAEs, SAEs, related TEAEs, TEAEs leading to discontinuation of trial medication, TEAEs leading to Death and AEs of special interest (AESI) will be calculated using the above algorithm.

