6. Females only; a urine pregnancy test will be performed at Screening, on Day 1 (Baseline), and all subsequent visits (does not include trial medication only visits).
7. Includes measurement of blood pressure, respiratory rate and pulse rate (all sitting after 5 minutes rest). The patient's body temperature will also be recorded.
8. Findings of alanine aminotransferase or aspartate aminotransferase >3 times the upper limit of normal or hemoglobin <8.0 g/dL at baseline are criteria for exclusion.
9. Two consecutive recordings need to be taken.
10. Adverse events will be collected from the time of informed consent. Adverse events continuing at the EoT Visit must be followed to resolution or follow up as agreed by the Investigator and medical monitor. For patients who complete the trial or who discontinue the trial early, AEs will be captured for 10 weeks after the EoT visit.
11. Questionnaires will be completed at the site by the patient before any investigations or discussions about their disease with the clinic staff.
12. Pharmacokinetic (PK) and anti-drug antibody (ADA) samples (including neutralizing ADA samples) should be taken at each visit designated with an "X", and can be taken at any time during the visit (PK and ADA/neutralizing ADA samples will be taken at the same time point). For all PK samples, the day and time of sampling must be accurately recorded. All dosing dates and times must be accurately entered in the patient diary. See also [Table 5.4: 1](#) for PK sampling time points.
13. At the Screening visit, the administration of BI 695501 will be performed by a suitably qualified, designated trial personnel at the site and patients will be trained on self-administration. This will be the last administration of trial medication in Trial 1297.2.
14. The first dose of trial medication in the extension trial will be administered at the Baseline visit, which is approximately 2 weeks after the Screening visit (the Week 48 visit of Trial 1297.2). The patients will self-inject BI 695501 with the support of the suitably qualified, designated trial personnel.
15. For all subsequent injections. Patients will self-inject the trial medication every 2 weeks until trial completion or early withdrawal.
16. 1 to 5 syringes will be dispensed to the patient at each visit.

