### **3.3.4 Removal of patients from therapy or assessments**

#### **3.3.4.1 Removal of individual patients**

Patients who do not meet all of the inclusion criteria or who meet one or more of the exclusion criteria will not be enrolled in this extension trial. The primary reason for the screen failure will be recorded on the electronic Case Report Form (eCRF).

Patients have the right to withdraw from this trial at any time for any reason.

Two situations can occur in this trial and need to be documented accordingly, as follows:

1. An individual patient is to be withdrawn from the trial if:
  - The patient decides to discontinue participation in the trial by withdrawal of consent. In this case, no more investigations will be performed. The patient does not have to justify the decision.
2. Based on assessment by the Investigator, and after consultation with the trial medical advisor, an individual patient may be discontinued from treatment with the investigational compound if:
  - The patient needs to take concomitant drugs that interfere with the investigational product or other trial medication
  - The patient can no longer be treated with trial medication for other medical reasons (such as surgery, adverse or drug-related events, other diseases, or pregnancy)
  - Repeated protocol violation after documented discussion with the medical monitor
  - Lack of efficacy
  - The patient has an AE that is categorized as a serious infection. A serious infection is defined as infections requiring i.v. antibiotics or those that meet the regulatory definition of a SAE (including, but not limited to, systemic fungal infections, human immunodeficiency virus [HIV], HBV, HCV, infected joint prosthesis)
  - Patient lost to follow-up despite reasonable efforts to make contact with the patient

If a patient permanently discontinues trial medication for any reason, every effort should be made for the patient to attend the EoT Visit as soon after trial treatment discontinuation as possible. Every effort should be made for all patients who discontinue the trial treatment early, to return for a safety follow-up visit 10 weeks after the last dose of trial medication. For details of assessments to be performed at the Week 48 visit and the Week 58 visit, see [Sections 6.2.2](#) and [6.2.3](#), respectively.

For all patients the reason for withdrawal (e.g., AEs) must be recorded in the eCRF. These data will be included in the trial database and reported.

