## 5.3.7 Adverse event collection and reporting

### AE Collection

The following must be collected and documented on the appropriate eCRF by the Investigator:

- From signing the informed consent onwards through the Residual Effect Period (REP), all AEs (serious and non-serious), and AESIs
- After the individual patient's end of trial: the Investigator does not need to actively monitor for AEs but should only report relevant SAEs and relevant AESIs of which the Investigator may become aware of

The REP for BI 695501 is defined as 10 weeks after the last trial medication application. All AEs which occurred through the treatment phase and throughout the REP will be considered as on treatment. Events that occur after the REP will be considered as post-treatment events.

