### **6.2.3 Follow-Up Period and Trial Completion**

#### End of Treatment Visit

Patients who discontinue the trial at any time after Day 1 (but do not withdraw their consent) will be required to have all of the evaluations for the Week 48 Visit as soon after trial discontinuation as possible.

Every effort should be made for all patients who complete the total 48-week treatment period or who discontinue the trial early, to return for a safety follow-up visit 10 weeks after the last dose of trial medication.

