## 9. DISPOSITION AND WITHDRAWALS

All subjects who provide informed consent will be accounted for in this trial.

The counts of the analysis sets will be presented:

- All Subject Enrolled (ENR)
- All Subjects Assigned (ASD)
- Safety Analysis Set (SAF)
- Full Analysis Set (FAS)
- Pharmacokinetic Full Analysis Set (PKFS)

The following subject disposition and withdrawals will be presented for the ENR set:

- Screened
- Screen failure (defined as subjects who do not enter the trial and are not assigned treatment), reason for non-inclusion
- Assigned to treatment
- Assigned to treatment but not treated
- Treated
- Completed treatment

---

Document: \\jeedc-nas01a\BIOSdata\Boehringer\_Ingelheim\BI\_695501\NVA96235\Biostatistics\Documentation\SAP\10  
v1.0\BI\_1297.3\_SAP\_22JUN2016\_v1.0

Author: Version Number: 1.0  
Version Date: 22JUN2016

Template No: CS\_TP\_BS016 – Revision 3  
Effective Date: 01May2012

Reference: CS\_WI\_BS005

- Completed trial
- Discontinued from treatment, reason for premature discontinuation from treatment
- Discontinued from trial, reason for premature discontinuation from trial
- Discontinued from safety follow-up, reason for premature discontinuation from safety follow-up

Subjects enrolment will also be summarized by country and by age group (18-64, 65-84, >=85).

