## 16.2. DEATHS

If any patients die during the trial as recorded on the completion or safety follow-up page of eCRF, the information will be summarized and listed.

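### SAP 16.1.1.2 credits every event-free patient with 70 days after treatment, even when death or the end of AE follow-up came sooner, so non-zero patient-year rates come out slightly low

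*SAP*

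**What the plan says.** SAP 16.1.1.2 divides the number of subjects with at least one qualifying AE by summed time at risk in years and multiplies by 1000. A subject with the event contributes time up to the first such event. A subject without it contributes "time at risk (days) = end of treatment + 70 – start of treatment +1". The same algorithm serves TEAEs, SAEs, related TEAEs, TEAEs leading to discontinuation or death, and AESIs.

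The 70 days are the protocol's residual effect period, and planned AE collection covers them:

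- Protocol 5.3.7 requires collection "From signing the informed consent onwards through the Residual Effect Period (REP), all AEs (serious and non-serious), and AESIs".
- Flow Chart note 10 adds: "For patients who complete the trial or who discontinue the trial early, AEs will be captured for 10 weeks after the EoT visit".
- Protocol 6.2.3 asks that every effort be made for completers and early stoppers "to return for a safety follow-up visit 10 weeks after the last dose of trial medication".

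The documents also foresee patients for whom this plan fails:

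- On withdrawal of consent, Protocol 3.3.4.1 says: "In this case, no more investigations will be performed".
- Loss to follow-up appears in Protocol 3.3.4.1 and in the end-of-trial definition in 6.2.3.
- SAP 9 has a disposition row: "Discontinued from safety follow-up, reason for premature discontinuation from safety follow-up".
- SAP 16.2 provides for deaths: "If any patients die during the trial as recorded on the completion or safety follow-up page of eCRF".

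None of these feeds into the time at risk.

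**The concern.** An event-free patient whose AE follow-up ended before last injection + 70 days still gets the full credit. The surplus days enlarge the denominator but bring no actively collected events. Death is the clearest case: a patient who dies within 70 days of the last injection, without the event in question, is credited with time at risk after death. The SAP respects that limit elsewhere, since Appendix 2 does not let an imputed AE stop date run past the date of death.

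With the events held fixed, the error has one direction: non-zero rates can only be lowered, which is the favourable direction in a safety trial. The rates are shown for the three Trial 1297.2 treatment sequences, so uneven follow-up would shift the groups by different amounts.

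There is also a smaller gap in wording. The formula does not define end of treatment. SAP 16.1.1.1 classes an event as post-treatment "if AE start date is strictly after the last injection date + 70 days", whereas Flow Chart note 10 counts its 10 weeks from the EoT visit, which in an early stopper comes after the last injection.

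**Working it through.** **Check of the rule itself.** With the first dose on Day 1 and the last planned dose on Day 337 (SAP 13), the formula gives 337 + 70 − 1 + 1 = 407 days. Visit 10 is planned for Day 407, so the rule is exact for a completer who is fully followed. A patient whose last dose is on day s is credited with s + 70 days.

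**Surplus for one patient.** If nothing is collected after the last dose, 70 days are surplus: 70/407 = 17% of the credit for a last dose on Day 337, 70/239 = 29% for Day 169 and 70/155 = 45% for Day 85.

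**Surplus across the trial.** The documents state no drop-out or follow-up rate, so the following inputs are all assumptions:

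- d = share stopping early, around day s
- u = share of early stoppers not followed after the last dose
- m = share of completers without AE status after Week 48

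For a rare event and a fixed numerator:

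- mean credited days = d(s + 70) + (1 − d) × 407
- mean surplus days = 70 × [d·u + (1 − d)·m]
- understatement of the rate = surplus / credited

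| Case | d | u | m | s | Surplus / credited | Understatement |
|---|---|---|---|---|---|---|
| Complete follow-up | any | 0 | 0 | any | 0 | 0 |
| Central | 0.15 | 0.50 | 0.05 | 169 | 8.225 / 381.8 | 2.2% |
| Central, all completers followed | 0.15 | 0.50 | 0 | 169 | 5.25 / 381.8 | 1.4% |
| Moderate, low end | 0.10 | 0.25 | 0.02 | 253 | 3.01 / 398.6 | 0.8% |
| Moderate, high end | 0.20 | 0.50 | 0.10 | 85 | 12.6 / 356.6 | 3.5% |
| Extreme corner | 0.30 | 1.00 | 0.10 | 85 | 25.9 / 331.4 | 7.8% |

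Two variants of the central case lower it slightly:

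- If unfollowed early stoppers are seen at an EoT visit 14 days after the last dose, it is 7.175/381.8 = 1.9%.
- If 20% to 40% of patients have the event, with mean onset on Day 100 to 150, it is 1.7% to 2.0%.

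**Cross-check with a simpler model.** Let a share q of all patients be unobserved after the last dose and credit everyone else with 407 days. For q = 10% and last dose on Day 169, the rare-event result is 7.0/(0.1 × 239 + 0.9 × 407) = 7.0/390.2 = 1.8%. Varying the last dose (Day 85 to 337) and the share with the event (1% to 40%) gives 0.7% to 0.9% for q = 5%, 3.0% to 3.9% for q = 20%, and 4.4% to 6.3% for q = 30%.

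**Scale.** The central case at N = 300 credits 381.8 × 300/365.25 = 313.6 patient-years, of which 6.8 are surplus (9.0 of 418.1 at N = 400). Seven event patients give 7/313.6 = 22.3 per 1000 patient-years, against 7/306.8 = 22.8 on capped time. The relative Poisson standard error is 1/√7 = 38%; with 70 event patients it is 1/√70 = 12%.

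**Undefined end of treatment.** If it is read as an EoT visit g days after the last dose in 15% early stoppers, the extra share of the denominator is 0.15g/(381.8 + 0.15g): 0.3%, 0.5% and 1.1% for g = 7, 14 and 28.

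**The case against.** The best defence is that the 70 days are the protocol's own risk window. Protocol 5.3.7 and 7.3.1 use it for the events and the SAP uses it for the denominator, so numerator and denominator match by design. That stands for every patient followed as planned. A reader might infer that the 70-day extension is itself wrong, or that time should stop at treatment discontinuation. The documents do not support this, because AE collection continues after treatment stops.

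A reader might also infer that the surplus days were wholly unobserved. That goes too far. After a patient's end of trial, Protocol 5.3.7 still asks the investigator to report relevant SAEs and AESIs that come to notice. Those days lack active collection, but a serious event in them can still reach the numerator. Days after death are a different matter and cannot be time at risk.

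It is also tempting to cut off the numerator at the same date. This could remove a known SAE from a safety rate. Suppose there are 5 SAE patients at N = 300, one known only from a passive report. The rate would fall from 5/313.6 = 15.9 to 4/306.8 = 13.0 per 1000 patient-years and would no longer match the subject count shown with it. With the numerator kept, it is 5/306.8 = 16.3.

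Finally, the size rests on assumption, and the analysis is descriptive with no hypothesis test. Both are true. They limit the weight of the point but do not make the denominator right.

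**Conclusion.** The point holds as a minor correction. As written, SAP 16.1.1.2 credits event-free patients with days after death or without active AE collection whenever follow-up ends before last injection + 70 days. For a given set of events, non-zero rates are then equal to or lower than the observed-time rates.

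The direction follows from the formula. The size does not, because it depends on drop-out that the documents do not give. It is about 1% to 4% under moderate assumptions, at most 2.2% in the central case, and zero with complete follow-up. The 7.8% corner needs 30% stopping around Day 85, none of them followed, plus 10% of completers without AE status. Even the central shift is small beside the sampling error of a rare-event rate.

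A reader might infer that the primary endpoint is biased. It is not: it is a number and proportion of patients and does not use this denominator. Counts, percentages and zero-event rates do not change either. Only the supplementary patient-year rates do.

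**What to change.** In SAP 16.1.1.2, for subjects without the event, set:

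time at risk (days) = min(last injection date + 70, date of death, last date of AE ascertainment) − start of treatment + 1

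The last date of AE ascertainment is the end of safety follow-up or the last contact. Three clarifications belong with it:

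- State that end of treatment in this formula means the last injection date, as in 16.1.1.1.
- Do not end time at risk at treatment discontinuation while AE follow-up continues.
- Leave the numerator and the formula for event subjects as they are. A subject with a qualifying TEAE, including one reported passively, stays an event subject with time up to event onset, so rates still agree with the displayed subject counts.

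The cost is a few lines of text and one derived date. The documents do not show whether the eCRF holds a last-contact date, so its source should be named. Rates become slightly less favourable. Where a passively reported event is kept while other patients' time is capped, the rate leans slightly upward, which is the cautious direction.
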